5.2 Randomization/Treatment Assignment

For the double-blind, vehicle-controlled phase of the study, subjects will be randomized at a ratio of 2:1 to receive tapinarof cream, 1% or vehicle cream as follows:

Randomization in Double-Blind, Vehicle-Controlled Phase	
Regimen	Number of Subjects
Tapinarof cream, 1% QD for 8 weeks	Approximately 267 Subjects
Vehicle cream QD for 8 weeks	Approximately 133 Subjects

QD = once daily

Randomization will be stratified by Baseline vIGA-AD™ score so that subjects with severe AD (vIGA-AD™ score of 4) will be limited to approximately 10% each of the total randomized population, and the majority of the enrolled subjects (approximately 90%) will have a vIGA-AD™ score of 3, signifying moderate disease.

Randomization will also be stratified by age so that a minimum of approximately 15% of subjects will be enrolled into each of the following age groups: 2-6 years, 7-11 years, 12-17 years, 18 years and above. Adults 18 years and above will comprise a maximum of 20% of enrolled subjects.

The randomization lists will be generated using a validated system, which involves a pseudo-random number generator so that the resulting treatment will be both reproducible and non-predictable. Access to the codes will be controlled and documented.

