10.2 Determination of Sample Size

It is estimated that the proportion of subjects who will achieve a vIGA-AD™ score of 0 or 1 and at least a 2-grade reduction from Baseline at Week 8 will be 45% for subjects receiving tapinarof compared with 25% for subjects receiving vehicle control, based upon the Phase 2 results. With 400 subjects randomized in a 2:1 ratio (267 subjects receiving tapinarof, and 133 subjects receiving vehicle control), this will provide 97.2% power for statistical significance (2-sided $p < 0.05$). The power is calculated from a Fisher Exact sample size calculation. It is assumed that 15% of the subjects receiving tapinarof will be lost to follow-up by 8 weeks compared with 30% of the subjects receiving vehicle control. These subjects will be included in the primary analysis using the multiple imputation method.

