10.4.2.2 Secondary and Exploratory Efficacy Endpoint Analyses

The secondary efficacy endpoints are as follows:

- Proportion of subjects with $\geq 75\%$ improvement in EASI from Baseline at Week 8
- Mean change in %BSA affected from Baseline at Week 8
- Proportion of subjects with $\geq 90\%$ improvement in EASI from Baseline at Week 8

- Proportion of subjects ≥ 12 years old with a Baseline PP-NRS score ≥ 4 who achieve ≥ 4 -point reduction in the PP-NRS from Baseline at Week 8

Exploratory efficacy endpoints are as follows:

The same methods as discussed for the primary analysis of the primary endpoint will be used to analyze all dichotomized secondary endpoints. The secondary efficacy endpoints will be tested sequentially in the order listed. Testing will stop if non-significance (2-sided $p \geq 0.05$) is observed.

Post-baseline weekly PP-NRS scores will be an average of 7 daily post-baseline PP-NRS scores prior to and including the values assessed on the visit date.

Other efficacy endpoints will be analyzed using CMH test for proportions, and analysis of covariance (ANCOVA) model for continuous variables. CMH tests will be stratified by Baseline vIGA-AD™ score and age group, and ANCOVA models will include vIGA-AD™ score and age group as categorical covariates and Baseline as a continuous covariate.

All endpoints will be summarized descriptively as follows: continuous data will include the mean, SD, minimum, maximum, median, and number of observations; descriptive summary statistics for categorical data will include frequency counts and percentages.

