6. GENERAL ANALYSIS CONSIDERATIONS

The statistical analyses will be reported using summary tables, listings, and figures (TLFs). The International Council for Harmonisation (ICH) numbering convention will be used for all TLFs. Unless otherwise noted, all statistical testing will be 2-sided and will be performed at the 0.05 significance level. Tests will be declared statistically significant if the calculated p-value is <0.05.

Continuous variables will be summarized by presenting the number of observations, means, standard deviations, medians, minimums, and maximums.

Categorical variables will be summarized by presenting counts and percentages of subjects in corresponding categories. All possible categories as defined in the case report form (CRF) should be populated, even if they have zero counts. Percentages for missing values are omitted and do not account for the percent calculation of other categories. Percentages are based on the total category count excluding the missing category if not otherwise mentioned. In certain tables (e.g., TEAEs), the total number of subjects is used as denominator. Footnotes will specify the percent basis in those cases.

All summary tables will be presented by treatment. Baseline summaries will also include a total summary column.

Individual subject data obtained from the eCRFs, external vendors, central clinical laboratory, ECG laboratory, pharmacokinetic (PK) data, and any derived data will be presented by subject in data listings.

The analyses described in this plan are considered a priori, in that they have been defined prior to database lock.

Any analyses performed after breaking the blind (after database lock, for unblinded studies) will be considered post hoc and exploratory. Post hoc analyses will be labeled as such on the output and identified in the CSR.

All analyses and tabulations will be performed using Statistical Analysis System[®] (SAS[®]) software Version 9.4 or higher. Tables, listings, and figures will be presented in rich text format (RTF).

The process for SAS program validation and quality control (QC) for programs and outputs is documented in the Synteract working instruction "SAS programming quality control." Study-specific QC requirements can be found in Appendix B: SAS programming QC requirements.

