11.2 Secondary Efficacy Analyses

The dichotomized secondary endpoints will follow the same composite variable strategy estimand (MI estimand) as the primary analysis of the primary endpoint.

For PP-NRS, if any day of the 7-day period used to compute the average weekly PP-NRS score is on or after the date of the intercurrent event, then the response will be considered a failure for the estimand analysis starting at that visit.

[figure not shown]
Mean change in %BSA will be analyzed with an ANCOVA with factor of treatment and age group*vIGA-ADTM score as a categorical covariate and baseline %BSA as a continuous covariate. The age group*vIGA-ADTM score covariate cohort is as follows:

age group:	vIGA-AD TM score	age group* vIGA-ADTM score cohort
2-6 yrs	3	1
2-6 yrs	4	2
7-11 yrs	3	3
7-11 yrs	4	4
12-17 yrs	3	5
12-17 yrs	4	6
≥18 yrs	3	7
≥18 yrs	4	8

[figure not shown]
The standard MI procedures (Section 10.4) for ANCOVA will be followed. Least squared means of treatment difference (tapinarof – vehicle) along with the 95% CI will be reported. Change from baseline will be assigned to 0 in a manner corresponding to assignment of non-response for the dichotomized secondary endpoints for subjects who discontinue treatment due to an AE or lack of efficacy and subjects who use prohibited medication with significant impact on efficacy evaluations prior to Week 8.

[figure not shown]
The secondary efficacy endpoints will be tested sequentially using the MI estimand analyses. Testing will stop if non-significance (2-sided $p \ge 0.05$) is observed as described in Section 10.7.

[figure not shown]

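### The %BSA ANCOVA is specified by covariates only, so at 267:133 its 95% CI has nominal coverage only if residual spread is equal in the two arms

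*Protocol*

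**What the plan says.** Protocol 5.2 states that "subjects will be randomized at a ratio of 2:1", and Protocol 10.2 gives the arm sizes as 267 tapinarof and 133 vehicle. Change in %BSA at Week 8 is the second of four secondary endpoints tested in sequence (Protocol 10.4.2.2, SAP 10.7), and SAP section 6 sets the level: "all statistical testing will be 2-sided and will be performed at the 0.05 significance level".

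For continuous endpoints the protocol says "ANCOVA models will include vIGA-AD™ score and age group as categorical covariates and Baseline as a continuous covariate". SAP 11.2 is more specific: "Mean change in %BSA will be analyzed with an ANCOVA with factor of treatment and age group*vIGA-ADTM score as a categorical covariate", with baseline %BSA as a continuous covariate and the crossed factor laid out as eight cells. It adds "The standard MI procedures (Section 10.4) for ANCOVA will be followed" and reports a least-squares mean difference with a 95% CI. Subjects counted as treatment failures have their change set to zero.

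No legible text in either document gives a residual variance by arm, a robust standard error, or a check of equal spread. The sensitivity analyses in SAP 10.4 (MI without the estimand rules, LOCF, observed cases, treatment failure) vary only the handling of missing data and intercurrent events.

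**The concern.** An ANCOVA described only by its factors and covariates is normally fitted with a single residual variance. With equal arms that choice hardly matters for the treatment contrast. With twice as many subjects on tapinarof, the pooled variance is weighted toward the tapinarof arm, while the true variance of the difference depends more on the smaller vehicle arm. If the two spreads differ, the standard error is wrong.

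There are reasons not to take equal spread for granted. %BSA is bounded below at zero, entry is restricted to 5% to 35% of body surface, response rates on the primary endpoint are assumed to be "45% for subjects receiving tapinarof compared with 25% for subjects receiving vehicle control", and the zero-change rule may apply to different shares of each arm. These features permit unequal spread. They do not settle which arm is the more variable.

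At stake is the stated precision of the %BSA treatment effect, which would be reported as a confirmatory secondary result. Exploratory continuous endpoints that use this model (SAP 10.3) have the same feature, but only their nominal intervals are affected. The CMH analyses of the primary and dichotomized secondary endpoints are not involved.

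**Working it through.** **Inputs.** n1 = 267 and n0 = 133 (Protocol 10.2); two-sided 0.05 (SAP section 6). The residual variance ratio k = vehicle / tapinarof is not in the documents. It is assumed here to run from 0.5 to 2.

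**The plan's own figure.** The documents state no figure for the %BSA analysis. The only stated figure on these inputs is 97.2% power for the primary endpoint. Exact enumeration of Fisher's test at 45% vs 25% gives 97.6%, and a continuity-corrected normal approximation gives 97.3%. That figure is not in dispute.

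**Closed form.** Set the tapinarof residual variance to 1.

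- True variance of the difference: 1/267 + k/133.
- Variance the pooled model reports, on average: [(266 + 132k)/398] × (1/267 + 1/133).
- R = square root of (pooled / true).
- Coverage = 2Φ(1.96R) − 1.

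Example, k = 1.5: true = 0.003745 + 0.011278 = 0.015024. Pooled = (464/398) × 0.011264 = 0.013132. R = √(0.013132/0.015024) = 0.935, so the standard error is 6.5% too small and coverage is 93.3%.

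| k (vehicle/tapinarof variance) | R at 267:133 | Coverage at 267:133 | Coverage at 200:200 |
|---|---|---|---|
| 0.5 | 1.119 | 97.2% | 95.0% |
| 1 | 1.000 | 95.0% | 95.0% |
| 1.25 | 0.963 | 94.1% | 95.0% |
| 1.5 | 0.935 | 93.3% | 95.0% |
| 2 | 0.894 | 92.0% | 95.0% |

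The last column shows that the distortion comes from the unequal allocation.

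**Check on the SAP model.** Treatment, the eight cells and baseline %BSA were simulated with complete data and normal errors, 20,000 runs per setting. HC3 is a heteroscedasticity-consistent standard error.

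| SD ratio tapinarof/vehicle | k | Coverage, closed form | Coverage, ordinary ANCOVA | Coverage, HC3 |
|---|---|---|---|---|
| 0.667 | 2.25 | 91.5% | 91.9% | 95.6% |
| 0.8 | 1.56 | 93.1% | 92.8% | 95.1% |
| 1 | 1 | 95.0% | 95.3% | 95.5% |
| 1.25 | 0.64 | 96.5% | 96.6% | 95.3% |

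**Multiple imputation.** PROC MIANALYZE combines the average squared standard error W with the between-imputation variance B as W + (1 + 1/100)B for 100 imputations. W is the squared model standard error, so an error in it carries through. In a simulation with the planned 15% and 30% missing, coverage stayed at 92% to 93% for k of 1.5 to 1.7.

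**What k might be.** In simulations with baseline %BSA of 5 to 35 and 45%/25% responders, k was 0.88 to 1.06 and coverage 94.8% to 95.5% when non-responders behaved alike in both arms. Adding zero change for 5% of tapinarof and 15% of vehicle subjects gave k = 0.94 and coverage 95.3%. Ratios of 1.5 or more needed a further assumption, namely that tapinarof non-responders also improve more or vary less than vehicle non-responders. The documents contain no figure for this.

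**The case against.** The strongest reply concerns direction. A reader might infer that tapinarof is pushed toward the zero floor, that vehicle is therefore more variable, and that the error favours tapinarof. The documents do not support that. A mixture of responders and non-responders is most variable near a 50% response rate. On the plan's rates the between-group term p(1 − p) is 0.45 × 0.55 = 0.2475 for tapinarof and 0.25 × 0.75 = 0.1875 for vehicle. Their ratio of 0.76, taken alone, makes tapinarof the more variable arm, with coverage of 96.0%. This stands.

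A reader might also infer that the %BSA test runs at 6.7% or 8.0% instead of 5%, the complements of the coverages at k = 1.5 and k = 2. Those figures require equal means with unequal spreads. Here the reason to expect unequal spread is itself a treatment effect: if tapinarof changed nothing, the spreads would match and the size would be 5%. In addition, %BSA is tested only after the primary endpoint and EASI-75 have succeeded. This also stands.

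Nor would the decision be likely to change. Simulated scenarios with k of 1.5 or more had a mean difference of about 5 or more standard errors, so a standard error 7% to 12% larger would not reverse the result.

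Finally, a pooled variance is inferred from the usual meaning of ANCOVA. Figures are missing around the ANCOVA text in SAP 11.2, and the example SAS code mentioned in the SAP revision history is not visible. That code is described as covering multiple imputation, so this limits certainty but does not answer the point. Reporting standard deviations by arm would reveal unequal spread without correcting the interval.

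**Conclusion.** The point holds as a statement about interval coverage. As written, the %BSA interval relies on equal residual variance in two arms of unequal size, and nothing legible in the plan supports or checks that assumption. Over k from 0.5 to 2, coverage runs from 97.2% down to 92.0%. It is 95% at k = 1, which is a plausible value. Both the ratio and its direction are assumptions. The calculations also assume that a single pooled variance is intended and, for the SAP-model check, normal errors and complete data.

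The point does not show a practical type I error problem, a bias toward tapinarof, or a likely change in the fixed-sequence outcome. It is of low severity, and worth making because the remedy is cheap and works whichever arm is more variable.

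**What to change.** In SAP 11.2, with a matching line in Protocol 10.4.2.2, keep the estimand and covariates and add one sentence on the standard error. In each imputed dataset, compute it either with residual variance estimated separately by arm (for example PROC MIXED with REPEATED / GROUP=treatment and Satterthwaite or Kenward-Roger degrees of freedom) or with a heteroscedasticity-consistent estimator. Pass that standard error to PROC MIANALYZE. The same code may be used for exploratory continuous endpoints analysed with this model.

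The cost is one code option and one sentence, with no change to design or data. The choice should be made before unblinding, because SAP section 6 treats analyses performed after the blind is broken as post hoc. The width of the interval changes by the factor 1/R: about 7% wider at k = 1.5 (1/0.935 = 1.070), 12% wider at k = 2 (1/0.894 = 1.119), and 11% narrower at k = 0.5 (1/1.119 = 0.894). With equal variances it is essentially unchanged.

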10.4.3 Safety Analyses

The Safety Population will be used in the analysis of safety data. Data will be listed by subject and treatment and summarized by treatment. No formal statistical comparisons will be made for safety data.

The number and proportion of subjects with TEAEs will be summarized by treatment, system organ class, and preferred term for all TEAEs, all TEAEs considered by the Investigator to be related to study drug, all SAEs, all TEAEs leading to study drug discontinuation, and all TEAEs leading to study discontinuation. All AE summaries will include information for AEs that occurred after administration of the first dose of study drug until completion of the final study visit. Data listings will be provided for subjects who discontinued the study due to an AE and for subjects with an SAE.

Laboratory values will be classified as normal, low or high based on normal ranges supplied by the laboratory. Changes from Baseline in abnormality status will be summarized using shift tables. For quantitative laboratory measures, observed values and changes from Baseline will be summarized descriptively by visit and treatment group.

Observed vital sign values (systolic and diastolic blood pressure, pulse rate, and body temperature) and change from Baseline in vital signs will be summarized similarly to the laboratory values.

Observed ECG parameters and change from Baseline in ECG parameters will be summarized similarly to the laboratory values.

LTS scores will be summarized by treatment and visit for subject (or caregiver) overall assessment and Investigator overall assessment separately.

10.4.4 Analysis of Functional Outcomes and Quality of Life Endpoints

- [REDACTED]
- [REDACTED]
- [REDACTED]
- [REDACTED]
- [REDACTED]

10.4.5 Pharmacokinetic Analyses

Data will be listed and summarized. Listings will be sorted by subject and day; summaries will be presented by study visit.

Unless stated otherwise, descriptive summaries for continuous variables will include n, mean, SD, median, minimum, and maximum. Exploratory analyses may include relationships of plasma concentrations with subject demographics or AEs.

10.5 Interim Analyses

No interim analyses will be performed.

10.6 Handling of Missing Data

Every effort will be made to collect complete data at all visits. The primary method of handling of missing data will utilize Multiple Imputations (MI). For sensitivity analysis of the primary and secondary endpoints, Last Observation Carried Forward (LOCF) and Treatment Failure (TF) will be imputed for missing data.

For the MI model, 100 imputations will be generated using PROC MI of SAS. Fully Conditional Specification model using the regression method will be used with the response (e.g., vIGA-AD™ score) at prior post-Baseline visits, Baseline strata, and treatment group as covariates. The ROUND and MINIMUM options will be utilized to ensure imputed values are non-negative integers. The results of the 100 analyses will be transformed into a normal statistic and combined into a single analysis using PROC MIANALYZE.

Additional sensitivity analyses of the primary endpoint will be performed via tipping point analysis.

11 Responsibilities

11.1 Investigator Responsibilities

11.1.1 Good Clinical Practice

The Investigator will ensure that this study is conducted in accordance with the principles of the “Declaration of Helsinki” (as amended in Edinburgh, Tokyo, Venice, Hong Kong, and South Africa), International Conference on Harmonization guidelines, or with the laws and regulations of the country in which the research is conducted, whichever affords the greater protection to the study subject. For studies conducted under a United States Investigational New Drug Application, the Investigator will ensure that the basic principles of “Good Clinical Practice,” as outlined in 21 Code of Federal Regulations (CFR) 312, subpart D, “Responsibilities of Sponsors and Investigators,” 21 CFR, part 50, 1998, and 21 CFR, part 56, 1998, are adhered to. These standards are consistent with the requirements of the European Community Directive 2001/20/EC.

Since this is a “covered” clinical trial, the Investigator will ensure that 21 CFR, Part 54, 1998, is adhered to; a “covered” clinical trial is any “study of a drug or device in humans submitted in a marketing application or reclassification petition subject to this part that the applicant or Food and Drug Administration relies on to establish that the product is effective (including studies that show equivalence to an effective product) or that make a significant contribution to the demonstration of safety.” This requires that Investigators and all sub-Investigators must provide documentation of their financial interest or arrangements with the Sponsor, or proprietary interests in the drug being studied. This documentation must be provided before participation of the Investigator and any sub-Investigator. The Investigator and sub-Investigator agree to notify the Sponsor of any change reportable interests during the study and for 1 year following completion of the study. Study completion is defined as the date that the last subject has completed the protocol-defined activities.

11.1.2 Institutional Review Board/Independent Ethics Committee Approval

This protocol and any accompanying material to be provided to the subject (such as advertisements, subject information sheets, or descriptions of the study used to obtain informed consent) will be submitted by the Investigator or on behalf of the Investigator to an IRB or IEC. Approval from the IRB or IEC must be obtained before starting the study and should be documented in a letter to the Investigator specifying the protocol number, protocol version, protocol date, documents reviewed, and date on which the committee met and granted the approval.

Any modifications made to the protocol after receipt of IRB or IEC approval must also be submitted to the IRB or IEC for approval before implementation.

11.1.3 Informed Consent/Assent

The Investigator is responsible for obtaining written informed consent/assent from each individual participating in this study after adequate explanation of the aims, methods, objectives, and potential hazards of the study and before undertaking any study-related procedures. The Investigator must utilize an IRB- or IEC-approved consent form for documenting written informed consent. Each informed consent/assent will be appropriately signed and dated by the subject or the subject’s legally authorized representative and the person obtaining consent.

11.1.4 Confidentiality

The Investigator must assure that subjects' anonymity will be strictly maintained and that their identities are protected from unauthorized parties. Only subject number, date of birth, and an identification code (i.e., not names) should be recorded on any form or biological sample submitted to the Sponsor, IRB or IEC, or laboratory. The Investigator must keep a screening log showing codes, names, and addresses for all subjects screened and for all subjects enrolled in the trial.

The Investigator agrees that all information received from the Sponsor, including but not limited to the Investigator Brochure, this protocol, CRFs, the investigational new drug, and any other study information, remain the sole and exclusive property of the Sponsor during the conduct of the study and thereafter. This information is not to be disclosed to any third party (except employees or agents directly involved in the conduct of the study or as required by law) without prior written consent from the Sponsor. The Investigator further agrees to take all reasonable precautions to prevent the disclosure by any employee or agent of the study site to any third party or otherwise into the public domain.

